### K3. Patient safety

If central study personnel become aware of new or worsening medical symptoms through information reported by patients during retention phone calls or during counseling sessions in the DM arm, they will refer the patient back to their PCP. Study laboratory results will be sent directly to the PCP per their standard operating procedures. Panic or critical value laboratory results will be managed per their standard operating procedures as well. All providers will be trained in SAE reporting during the central training and in ongoing discussions with the practice throughout the course of the study. Overall management of diabetes, hypertension, cardiovascular disease, and other medical conditions remains under the control of the treating PCP. The treating PCP, in communication with the KUMC PI and study physician, will determine if it is unsafe for the participant to remain in the study based on a change in medical status.

***Exercise-related AEs.*** If a cardiovascular event occurs during prescribed exercise, the physical activity component of the intervention may be suspended and/or later resumed with possible modifications after approval from the treating PCP. For exercise-related events and injuries for patients in the DM arm, the study clinician and/or the treating PCP will be consulted according to the symptoms reported. If appropriate, the participant’s exercise goals or type will be modified. If the symptoms or injury do not resolve after an appropriate period of time, the participant will be referred to his or her PCP for further evaluation and may

be removed from the study. In the FFS and PCMH arms, management of any non-serious exercise-related AEs remains under the control of the PCP.

*Diet-related AEs.* If participants suffer negative health consequences from consuming nutritionally inappropriate diets (such as rapid weight loss, gallstones) and counseling to change nutritional intake have been ineffective, the treating PCP (in consultation with the central counselors for the DM arm) may decide to suspend the intervention. This scenario is uncommon but may occur.

### **III. SUBJECT PARTICIPATION**

#### **A. Recruitment**

##### **A1-2. Recruitment location and personnel**

The primary method of recruitment will be through mailings of a study invitation and brochure from the PCP. This method is necessary to reach patients who otherwise would not visit the practice during the recruitment window, i.e., if we relied solely on recruitment during routine visits to the clinic we would risk a bias toward selecting patients with greater medical co-morbidities. This recruitment method also allows us to track and evaluate the enrollment rate and representativeness of participants.

Each practice will develop a registry of patients with a BMI in the target range. Providers may review the registry to identify and exclude patients who may be inappropriate (e.g. terminal cancer, communication disorders, other medical contraindications). The mailing will include an invitation letter on practice letterhead, signed by the provider, a study brochure (which will include the study phone number and the web address for our study website), and a pre-stamped, opt-in post card for those who prefer to receive a phone call. The letter will ask interested patients to contact the study line or return the post card. Patients will also have the option of contacting the study team via a contact link on our study website. In our current R01 trial in the rural setting, the opt-in postcard had a higher response rate and higher enrollment rate compared to relying on patients to make the initial call. The mailing will be assembled by central study team with an approved HIPPA waiver. Practices may elect to assemble the mailing themselves, however our experience indicates it will not be feasible for busy practices.

Recruitment will also occur through in-clinic approaches. Study brochures will be distributed at various places in the clinics (passive approach), and providers will be able to directly refer patients during routine medical visits (active approach). Study brochures will contain a link to our RE-POWER website containing basic study information. The website will be contained within the KUMC system and is being developed with the help of KUMC Information Technology personnel. Clinic staff will instruct interested patients to contact the central recruitment and screening line. If practices have difficulty attaining their stated goal of 40 patients, additional recruitment efforts may be utilized to identify patients. Examples of these additional avenues include the use of press releases/news briefs in local newspapers, on practice websites and Facebook pages; placement of referral posters in the local community, and/or welcoming existing study participants to refer their acquaintances who go to the same clinic by sharing the study line.

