## **C2. Blinding**

Randomization happens at the practice level. Blinding practice staff or study staff is not feasible during a behavioral trial. However, throughout the study investigators and study personnel will communicate and

demonstrate equipoise (genuine uncertainty) with practice staff and patients about the relative benefit of the three arms.

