### **D2. Exclusion criteria**

As a pragmatic trial, the exclusion criteria were kept minimal to maximize generalizability and reduce patient screening burden but include necessary exclusions to minimize safety concerns and major confounds on the primary endpoint. Individuals with a history of bariatric surgery or planned bariatric surgery within 2 years, myocardial infarction (MI) in the last 6 months, stroke in the last six months, new cancer diagnosis in the last six months (with the exception of non-melanoma skin cancer), pregnancy in the last 6 months/planned within the next 2 years or currently lactating, and serious medical conditions where weight loss is contraindicated will be excluded from the study. A history of miscarriage in the last 6 months, in and of itself, will not be considered an exclusion. Individuals with end stage renal disease, known GFR < 25, current or anticipated dialysis or transplant within the next two years will be excluded; a history of renal transplant is not an exclusion per se if patient does not meet stated renal criteria. Similarly, patients with end stage liver disease or anticipated liver transplant within the next two years will be excluded; a history of liver transplant is not an exclusion per se, if patient does not meet stated hepatic criteria. Other medical contraindications will be determined by the patient's PCP, and documented PCP clearance will be obtained. Participants who are already enrolled in, or planning to enroll in another research study where weight loss is targeted will be excluded. Participants who plan to relocate outside of their provider's service area or who

plan to leave their primary care clinic in the next two years will be excluded. Participant eligibility screening, assessments, and counseling sessions will be delivered in English; individuals who do not speak English will be unable to participate in the study.

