PCP and Counselor Training	
 
• Half-day training on assessing and treating obesity
 
• IBT toolkit including session guide and patient hand-outs modeled after 5 A's approach, instructions for dietary assessment and feedback, and web-based resources
 
	
 
• Half-day training on assessing and treating obesity
 
• For care coordinators/counselors: 
 
○ Full-day workshop on group visits
 
○ Bi-weekly to monthly telementoring
 
○ Standardized session-by-session treatment manual
 
 
 
	
 
• Half-day training on assessing and treating obesity
 
• For obesity treatment specialists: 
 
○ Relevant graduate degree and experience with weight loss counseling
 
○ Weekly training/quality control
 
○ Fidelity monitoring of audio-recorded sessions
 
 
 
• Standardized session-by-session treatment manual
 

Office Support/ Practice Facilitation	Assistance with: 
 
• developing patient registry
 
• identifying appropriate practice staff to deliver counseling sessions
 
	Assistance with: 
 
• developing patient list
 
• design and conduct of group visits
 
• identifying appropriate practice staff to deliver counseling sessions
 
• developing systems to track group visits and email/text contacts
 
	Assistance with: 
 
• developing patient list
 
• integrating progress reports from remote provider into electronic medical record
 

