**Practice facilitation.** To assist practices with implementing study-related activities, a Practice Coordinator (central study personnel) will provide practice facilitation to clinics in all arms, working directly with a Practice Liaison (primary contact) at each clinic. Practice facilitation is an effective strategy for improving care delivery through the creation of an on-going, trusting relationship with an external facilitator who works with the practice on workflow redesign and quality improvement. The workflow issues that require practice facilitation will vary across arms as well as from one practice to the next. Practice Coordinators will work closely with clinics in all arms prior to study implementation to assist with developing a registry of patients with a BMI > 30 kg/m^2, assure that office personnel have received appropriate training that workflows are in place, and that intervention tools and tracking tools are ready for participant visits. Practice Coordinators will conduct additional in-person follow-up visits to each clinic approximately once each year; additional visits will be conducted as needed to ensure adequate training and study progress.

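### Unblinded providers may strike registry patients before the mailing under an open list that goes beyond the eligibility criteria, with no record of removals and no stated order relative to disclosure of the arm

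*Combined protocol and SAP*

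**What the plan says.** Section II.D2 states that "the exclusion criteria were kept minimal to maximize generalizability and reduce patient screening burden". It leaves some room for judgement, but with a record: "Other medical contraindications will be determined by the patient's PCP, and documented PCP clearance will be obtained".

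Section III.A1-2 describes an earlier, optional step. Before invitations are mailed, "Providers may review the registry to identify and exclude patients who may be inappropriate (e.g. terminal cancer, communication disorders, other medical contraindications".

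On allocation, II.C2 says "Randomization happens at the practice level" and "Blinding practice staff or study staff is not feasible during a behavioral trial". On the registry, II.E2b says "Practice Coordinators will work closely with clinics in all arms prior to study implementation to assist with developing a registry". Table 1 lists this help by condition: "developing patient registry" stands in the FFS column, and help with a patient list stands in the PCMH and DM columns.

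Table 6 (II.E2f) sets out the reach measures. They include the percentage of registry patients who enroll, a comparison of enrollees with the original registries at the ten Marshfield practices, and, at all sites, a comparison of enrollees with patients on the mailing lists who do not enroll.

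**The concern.** In a cluster trial, patients are usually identified by people who may already know the arm. Anything discretionary at that stage can shape who enters each arm, and randomizing practices does not protect against it. The registry review is discretionary, its list of reasons is open, and it leaves no described trace.

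The arms also differ in ways that could bear on the judgement. Table 1 gives 15-minute individual visits in FFS, 60-minute groups in PCMH (in person for the first four months, then in person or by phone) and 60-minute phone groups in DM. A provider who thinks a patient would struggle in a group, or on a group call, might strike that patient in one arm and keep a similar one in another.

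Two things are at stake: comparability of the arms on traits that baseline variables may not capture, such as expected adherence, and the representativeness data that the mailing method was chosen to provide.

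**Working it through.** **1. The examples in III.A1-2 against the eligibility rules**

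- Terminal cancer: plausibly covered by II.D2, through serious conditions where weight loss is contraindicated or through the PCP's judgement.
- Other medical contraindications: covered by II.D2.
- Communication disorders: in neither II.D1 nor II.D2. The nearest rules are language ("individuals who do not speak English will be unable to participate in the study"), telephone access (II.D1) and ability to consent (III.C3). A hearing or speech problem is none of these.

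So one of the three examples goes beyond the eligibility section, and the list is not closed.

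**2. What is recorded at each step**

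- Eligible but unable to attend the arm's visits: reason recorded (II.D1).
- PCP clearance: documented (II.D2).
- Ineligible measured BMI: entered in the database (III.C1).
- Struck from the registry: no count, list or reason described.

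**3. Order of review and disclosure of the arm**

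The order is not stated. Table 1 lists registry help by condition, II.D1 refers to arm-specific visits at screening, II.I4 has consent forms that vary by arm, and II.E5 gives FFS nine months to enroll against six for the other arms. These suggest that the arm is known when the registry is reviewed. Against that, II.I3 requires practices to show that they can build a registry before they commit. Nothing requires the review to be finished before the arm is known.

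**4. Would existing checks show it?**

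The enrollment percentage uses a registry denominator, but Table 6 does not say whether that is before or after strikes. Only the Marshfield comparison names the original registry. At the other 36 − 10 = 26 practices, the demographic comparison uses the mailing list, which is formed after strikes. The confounder sensitivity analysis in II.C1 uses baseline variables of enrolled patients only.

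**5. Size: patients affected**

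From the documents: registry of 300 to 400 (II.I3), 40 enrolled per practice (II.C3). Assumed: a strike rate s of 5 to 10%, and struck patients who would have enrolled at the same rate as those left.

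Would-be enrollees struck = s × R × 40 / [R × (1 − s)] = 40 × s / (1 − s). The registry size R cancels.

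- s = 5%: 40 × 0.05 / 0.95 = 2.1 per practice
- s = 10%: 40 × 0.10 / 0.90 = 4.4 per practice

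**6. Size: effect on the comparison**

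The plan's power first, for its standard error (II.C3: 480 per arm, ICC 0.05, SD 8, 2.75 kg, two-sided 0.025, normal approximation):

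- Design effect = 1 + 39 × 0.05 = 2.95; effective n = 480 / 2.95 = 162.7 per arm
- SE = 8 × √(2 / 162.7) = 0.887 kg
- Power = Φ(2.75 / 0.887 − 2.241) = 80.5%, against 80% stated

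Let q be the between-arm difference in the share of would-be enrollees struck, and g the difference in 24-month weight change between those patients and the rest. Neither is in the documents. Bias b ≈ q × g, and the type I error per comparison is 1 − Φ(2.241 − b/SE) + Φ(−2.241 − b/SE).

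| q | g (kg) | b (kg) | % of 2.75 | Type I error |
|---|---|---|---|---|
| 2% | 1 | 0.02 | 0.7 | 0.025 |
| 5% | 2 | 0.10 | 3.6 | 0.026 |
| 5% | 4 | 0.20 | 7.3 | 0.029 |
| 10% | 4 | 0.40 | 14.5 | 0.040 |

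**The case against.** The strongest reply has four parts.

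- **A strike is not a trial exclusion.** It removes a patient from the mailing. III.A1-2 also provides for brochures in the clinic, direct referral and, if needed, local publicity, and no text bars a struck patient from these. This stands, and it reduces the effect.
- **Reach is partly monitored.** Table 6 has the registry percentage and the Marshfield comparison, and II.C1 compares participation rates across arms. This stands too. None of these records strikes or reasons, and the demographic gap at 26 practices remains.
- **The arm mechanism is conjecture.** Every arm has telephone screening (III.B), required telephone access and English-language sessions, so a communication disorder bears on entry in all three. This stands as a caution: differential striking is possible, not shown, and no direction can be given.
- **The fix is partial.** The same unblinded providers later give clearance (III.C1) and can refer patients directly. This is true. It limits what the change achieves but is no reason to leave this step open.

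A reader might go further and infer that the review is known to follow disclosure of the arm. The documents do not say so; Table 1 only makes it likely.

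**Conclusion.** The point holds as a weakness in a stated rule. III.A1-2 allows an unrecorded, open-ended removal of patients by unblinded providers, with one example outside II.D1 and II.D2 and no stated order relative to disclosure of the arm. Removals could differ by arm; the documents do not show that they do.

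The size cannot be derived from the documents. At an assumed 5 to 10% strike rate, about 2 to 4 would-be enrollees per practice are affected, fewer if some enter by other routes or would have failed clearance anyway. It is tempting to set the 15 to 40 struck patients (5% of 300 to 10% of 400) against the 40 enrolled, as if a practice could lose its whole sample. These are different populations: most registry patients never enroll.

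Over the assumed values of q and g, the bias is 0.02 to 0.40 kg against the planned 2.75 kg, and the type I error 0.025 to 0.040 against 0.025. That is modest. The plan's power calculation is not in question. The change is worth making because it is cheap and closes a selection channel that the planned analyses could neither detect reliably nor adjust for.

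**What to change.** In III.A1-2:

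- Limit provider review to the II.D2 criteria, including medical contraindications judged by the PCP. Reconcile communication disorders with II.D2 so that one rule applies in all arms.
- State that the review is completed and the mailing list locked before the practice is told its arm.
- Record one reason code per removal and report removals by practice and arm.

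In Table 6, define the reach denominator as the registry before removals and, where data allow, use that registry as the comparator at all sites.

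If mailings have already gone out, compare any retained original registries with the mailing lists, by practice and arm, and report the result.

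The cost is a change in the order of start-up steps, a one-column log, and some letters to patients who are later screened out by phone or at clearance. PCP clearance and direct referral by unblinded providers remain as separate channels, and the report should say so.

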##### **A3. Copy of recruitment brochures**

See Attachments

##### **A4. Copy of participant recruitment letter and opt-in postcard**

See Attachments

## **B. Screening Interview**

KUMC study personnel will screen potential participants who call the study line or return the opt-in postcard. These personnel are trained in human subjects research and are experienced in clinical trial recruitment and screening. They will inform patients about the study, obtain verbal assent for eligibility assessment, and then screen for eligibility by phone. See attachment for the screening questionnaire.

## **C. Informed Consent Process and Timing of Obtaining Consent**

### **C1. Obtaining consent**

If deemed eligible for the study following the telephone screening, the patient will have the option of receiving an email with a link to the baseline survey consent form or a hard-copy consent/survey via mail. The baseline survey consent will include information about the purpose of the baseline survey. The consent will indicate agreement to complete the survey is separate from giving full consent for the trial. Participants must complete the baseline survey in order to be enrolled in the study.

After a patient completes the baseline survey, medical clearance will be obtained from their primary care provider or lead physician at the practice. Practice personnel will then schedule for the patient for the consent/baseline visit at the practice. Patients must complete the consent/baseline visit within 60 days of the phone screening.

At the consent/baseline visit, informed consent for the full trial will be administered. Practice staff will give detailed and comprehensive information about the 2-year trial and answer all patient questions.

Practices will be encouraged to verify BMI prior to consenting patients. BMI verification may, however, occur before or after consent depending on practice workflow. If a patient is ineligible based on measured BMI, but is within 0.5 BMI points (3-5 lbs), the patient may elect to return for BMI verification after a minimum of one week. If a patient is ultimately ineligible based on BMI verification, the patient will be considered a screen-fail. The ineligible BMI status will be documented in the study database, and the patient will not be enrolled in the study. Signed consent forms for both eligible and ineligible subjects will be retained.

### **C2. Consent process**

Consent will occur in-person at the participating practice with trained practice personnel. A brief video will be available to help standardize the consent process, and practice personnel will be present to answer questions. The consent process will include explicit indications (verbal and written) that participation is always voluntary, and that patients are free to leave the study at any time with no consequences for their routine medical care at the local practice or affiliated institutions (KUMC, UNMC, Marshfield Clinic). All participants will receive a signed copy of their signed trial consent form. A copy of the signed consent will be placed in the patient's medical record at the practice. Practices will fax or secure email copies of the consent to KUMC within approximately two business days, or upload a copy of the consent into the secure study database, REDCap. Original consent forms will be retrieved from the practices by central study staff or mailed to KUMC in pre-addressed envelopes provided to them, or to UNMC or Marshfield Clinic study personnel who will then forward to KUMC. All original hard copy consents will ultimately be maintained at KUMC in a secure locked file cabinet.

### **C3. Ability to give informed consent**

Participants' ability to give informed consent will be assessed 1) by KUMC staff conducting eligibility screenings and baseline surveys, 2) the primary care physician or lead physician at the practice prior to the consent visit, and 3) by the clinic staff administering the consent during the baseline/consent visit. Those with compromised ability to consent will not be enrolled.

#### **C4. Patient retention protocol**

**As a pragmatic trial, we will not implement stringent retention protocols to improve retention to counseling visits, and we expect differential attendance across arms. However, we will implement retention contacts to ensure adequate retention to assessment visits.**

The REDCap scheduling forms will specify date ranges for assessment visits. Designated practice staff will use the REDCap scheduling form as a guide to schedule study visits into the practice's preferred scheduling software (e.g. their EMR, practice management tool and/or REDCap). Practices will utilize their own appointment reminder system as available. Practices may opt to send automated text messages and/or emails to patients to remind them of upcoming visits. If participants do not have access to email, practice staff will be prompted by REDCap report to call patients to remind them of their upcoming assessment visits. KUMC study staff will work with the practices to define the most efficient and productive manner of conducting appointment reminders with the means available through the practice and REDCap capabilities.

Practice Coordinators will work closely with the Practice Liaisons to follow-up with participants who miss an assessment visit. After failed contact attempts by the practice, KUMC study personnel will take over attempt to contact and reschedule the patient. Retention will be monitored and discussed in a weekly project management meeting among KUMC staff. Practice Liaisons will be contacted as needed to trouble shoot retention strategies at the practice level. For patients who miss an assessment visit, attempt will be made to capture missing weight data from chart review.

